### **Inclusion/Exclusion Criteria**

*Inclusion criteria:* Registered with one of participating General Practices; aged 65 or more; score as 'mild frailty' on the Clinical Frailty Scale; community-dwelling (including people living in extra care housing); life expectancy > 6months; capacity to consent to participate in this research (including those with dementia or communication difficulties who retain capacity to consent). We will include participants who are not able to communicate in English, if they can provide informed consent, assisted if needed by a translator.

**Exclusion criteria:** Those living in care homes (likely to have established frailty); on GP palliative care register; those who lack capacity to consent (e.g. advanced dementia); those already case managed (e.g. by community matrons, some reablement schemes).

### **Setting/context:**

Participants will be community dwelling and recruited through General Practices in Hertfordshire and the London Borough of Camden.

# 12. Search strategy

### **Systematic reviews:**

We will use Cochrane systematic review methods, and identify components associated with effectiveness; what works, for whom, why? We will write and publish a formal protocol for the reviews. For the qualitative and policy review we will additionally be guided by the methods developed by the Social Care Institute for Excellence and National Centre for Clinical Excellence (NICE) for synthesis of heterogenous literature for NICE Public Health guidance. We do not aim to replicate other recent systematic reviews of RCTs, such as Tappenden et al but will update this review with any trials published since March 2011, broaden the scope to include trials of interventions delivered by any health professional at home (not restricted to nurses) and focus specifically on identifying components within interventions associated with effectiveness. In addition we will conduct a systematic review of qualitative studies focusing on defining active ingredients and the acceptability and feasibility of different modes of intervention delivery for older people. This will include i)

any linked qualitative studies to the RCTs identified and ii) qualitative studies of older people with early or pre-frailty and their perspectives of health promotion and behaviour change interventions.

Studies of home-based interventions will be identified via a systematic database search for the period 1990 to present of MEDLINE, MEDLINE in Process & Other Non-Indexed Citations, EMBASE, Science Citation index Expanded (SCIE), Cochrane Database of Systematic Reviews (CDSR), Cochrane Central Register of Controlled Trials (CCRCT), Cochrane Effective Practice and Organisation of Care Group (EPOC), PsycINFO, Health

Technology Assessment (HTA) database, NHS Health Economic Evaluation Database (NHS EED), Health Economics Evaluations Database (HEED), Database of Abstracts of Reviews of Effects (DARE), Cumulative Index to Nursing and Allied Health Literature (CINAHL); Evidence for Policy and Practice Information Centre Register of Health Promotion and Public Health Research (BiblioMap), Sociological Abstracts (SocAbs), Applied Social Sciences Index and Abstracts (ASSIA), Health Development Agency Register (Health Promis), Index to Theses. Completed and unpublished studies will be identified through searches in the HTA database, the UK Clinical Research Network (CRN) Portfolio Database and ClinicalTrials.gov. Leading researchers in the field will be contacted to help identify unpublished research or work in press. Intervention descriptions will be obtained from published journal papers and unpublished materials (protocols, manuals) requested from corresponding authors. Preliminary searching will begin with a strategy based on keyword/index (MESH) terms. In addition 'lateral searching' techniques will be used including checking reference lists of relevant papers, using the 'Cited by' option on Web of Science, Google Scholar and Scopus, and the 'Related articles' option on PubMed and Web of Science.

In addition to the above databases we will conduct a rapid appraisal of the policy context, searching national, local government and local health care provider and commissioning groups websites, and other relevant resources e.g. Health Promotion and Public Health Research (BiblioMap), addressing the context issues in introducing and sustaining innovation in health care. This search will use key words derived from the study objectives. Key people in central, regional and local government organisations will be contacted to assist in the identification of relevant documents, as well as leading figures in national level voluntary and professional organisations.

# 13. Sampling

### Qualitative study:

In depth interviews: We will use data from our current study (MRC funded WISH Study) of interviews with 52 older people and stakeholders from the NHS (GPs and practice nurses), local government (adult social care, housing and transport), public health/commissioning, the voluntary sector (local AgeUK, U3A, and other smaller organisation representatives) which explore approaches to health promotion for older people, barriers/facilitating factors and views on content/delivery of health promotion for older people. In addition we will supplement this with up to 10 interviews on home-based health promotion with older people who are unable to leave their homes, who are not well-represented in our current study. We will sample for maximum diversity with respect to age, gender, socio-economic status and ethnicity and aim to achieve saturation on main themes. Participants will be identified from General Practices in North and Central London/Hertfordshire. Focus groups: In order to explore further key stakeholder perspectives on health promotion interventions for older people with early frailty we will conduct 4 focus groups with 1) carers of people with early frailty, 2) home care workers and 3) two groups with community health professionals (district nurses, community occupational therapists, community physiotherapists, Health Trainers and community matrons), with up to 8-10 participants in each group. Carers will be

identified through participating General Practices and carers' groups/organisations. Carers will be given an option of attending a focus group or of having a one-to-one interview in their home if more appropriate (e.g. if they are a carer of an older person who is already being interviewed at home). Home care workers will be identified and invited through their employers (with whom we have good contacts) and representative organisations e.g. Hertfordshire Care Providers Association, and community health professionals through our collaborators in Camden and Hertfordshire Clinical Commissioning Groups, and community health service providers.

# Feasibility study:

Sampling strategy: We will select 2 practices each in our 2 study areas (London Borough of Camden and Hertfordshire) to ensure a diverse representation of older people living in urban, suburban, and rural communities and from diverse socio-economic and ethnic backgrounds. The London Borough of Camden has a very socially and ethnically diverse population, while there are higher proportions of older people (and very old people) in Hertfordshire with differences in access to health, transport and other services. Participants will be identified through database searches of GP lists of registered patients over 65, excluding those with recorded exclusion criteria (e.g. those on the GP palliative care register). These lists will be further screened by participating GPs for eligibility criteria and exclusions removed. Remaining participants will be approached by letter by their GP with a study information leaflet. A telephone reminder will be made to non-responders by a member of the practice team. Those expressing an interest will be contacted by the research nurse for initial telephone eligibility screening. GPs will also be able to refer people opportunistically to the study, e.g. those they are visiting/have visited at home recently who did not meet criteria for existing frailty services. Potentially eligible participants (from telephone screening or GP referral) will then be visited at home to discuss participation, gain informed consent, full baseline assessment, and subsequent web-based randomisation.

Sample size, recruitment and retention: For the feasibility study we aim to recruit 50 people, 12-13 each from 4 General Practices. This number was selected as a sufficient number to test the feasibility/ acceptability of the intervention and pilot the study process, recruitment, randomisation and retention for a full RCT, and a realistic number to recruit per practice and deliver the intervention in the short time frame available for the feasibility study. Assuming an average of 600 people aged over 65 per study practice (based on our previous studies with this age group in our study settings), a prevalence of 41% of 'pre-frailty'38 would lead to a population of 246 before exclusions. Assuming (on best estimates) 30 of these are excluded, and 20% have been visited at home in the last 6 months by a health professional (including GPs, Out of Hours services, nurses, health care assistants, physiotherapist, occupational therapist or other community health professional) our eligible population would be 43 people. Assuming a conservative recruitment rate of 30% of eligible people, we could recruit 13 people per practice. In our past experience in previous studies on health promotion in the 65+ population (the WISH study) our attrition (including deaths) over 3 months was 10% and over 6 months 23%. Part of the purpose of the feasibility study is to assess if all of these assumptions are correct, as there is no data available (apart from community prevalence) that are specific to an older population with early frailty with which to base these assumptions. If our eligibility or recruitment rate is much lower than anticipated we would be able to extend our study to include further GP practices.

# 14. Data collection

### **Systematic reviews:**

Research studies identified by the systematic searches will be grouped into RCTs/systematic reviews of RCTs and qualitative, observational and quasi-experimental studies. Identified abstracts and items will be screened against the agreed inclusion and exclusion criteria by two researchers. Full

text copies will be retrieved, read for those meeting the criteria or are ambiguous. Documents and data will be managed through bibliographic software and electronic spreadsheets. Data extraction formats will be developed for each of the types of evidence (e.g. RCT, qualitative) and relevant to the research questions. Quality assessments will be made of research studies according to the type of evidence, using Cochrane methods for RCTs and SCIE/NICE methods for the qualitative studies.

### Qualitative study:

Topic guides will be developed for in-depth interviews with older people and focus groups based on the literature review findings and findings from our current WISH qualitative study. They will explore attitudes towards health promotion and behaviour change for older people with early frailty, experiences of behaviour change attempts, barriers and facilitating factors, and views on the content and delivery of a home-based health promotion intervention (e.g. who should deliver it, what it should contain, how often etc). In depth interviews with older people will be conducted in participants' homes, and be recorded and transcribed verbatim. Focus groups will be conducted in an accessible local venue with an experienced facilitator from the research team and an observer present recording field notes, and will be recorded and transcribed verbatim. Refreshments will be available and travel costs met.

### **Intervention development:**

The intervention will be informed by insights from the systematic review and the qualitative study. The systematic review will extract components found to be associated with effective previous interventions, while the qualitative study will identify the needs of the target population within which intervention content must be contextualised. Hence, our intervention will marry a top-down, theory-driven approach with a bottom-up, experiential approach. The research team will synthesise inputs from the two evidence sources in an integrative review using thematic analysis so as to develop an intervention that uses components previously found (via the systematic review) to be associated with effectiveness, as framed by the needs of the target population (as identified via the interviews and focus groups).

The research team's initial ideas for the intervention, as informed by the reviews and qualitative work, will be used as a basis for discussion among the research team and the co-designers. The co-design development panels will be presented with a summary of the evidence and the research team's views on the intervention content, theory and behaviour change techniques, based on this evidence. The co-designers' expert knowledge and interpretation of the available evidence and experiences will be used to inform the most appropriate intervention delivery method and to tailor the intervention to those people with early frailty. This is important as we anticipate that much of the RCT evidence will relate to older populations more broadly. These discussions will inform refinement of the intervention, while retaining the key intervention components (identified in the systematic reviews) and addressing the needs identified (via qualitative review and interviews/focus groups). The research team would lead on developing the intervention based on these discussions. Each refinement of the intervention would be discussed with co-designers, such that multiple iterations of the intervention may be proposed. The final version will be approved by the research team and co-designers and at this point we will proceed to the feasibility study.

### Feasibility study:

We will randomise individual participants to intervention or treatment as usual (TAU) arms to assess willingness to be randomised and check for contamination with patients in the same practice. We have full support of PRIMENT CTU, including a randomisation service, SOPs, database and quality assurance. We will use an independent web-based randomisation service through PRIMENT CTU. The researcher conducting outcome assessments will be blind to treatment group. Data will be collected at baseline, 3 months and 6 months.

Outcome measures: Potential outcomes for a main RCT including: quality of life (EQ-5D), functioning (modified Barthel), frailty (Frailty Index of cumulative deficits), mobility (gait speed), grip strength, well-being (Warwick-Edinburgh Mental Well-being Scale), psychological distress (GHQ-12), CVD risk factors (BMI, physical activity- IPAQ, smoking, alcohol AUDIT-C), medication use, cognitive function (MoCA) service use (Modified Client Services Receipt Inventory-CSRI), QALYs, Capability (ICECAP-O); mortality. Resource use will be costed using national reference costs.

*Process evaluation:* We will collect data on eligibility, uptake/recruitment and non-respondents where possible at each stage, and adherence, attrition/losses to follow-up and document these in a CONSORT flow diagram^75. Intervention appointments will be audio-recorded and a random sample of 10% checked for fidelity to the intervention. We will conduct a process evaluation with questionnaires for all feasibility study participants and semi-structured interviews with a purposive sample of up to 15 participants receiving the intervention, sampled from those with good/poor adherence/outcome from the intervention.

# 15. Data analysis

### **Systematic reviews:**

Interventions identified from the searches of RCTs will be coded according to seven dimensions: intervention content (behaviour change techniques, theory-base, intervention function), format (methods of intervention administration), setting (where and when delivered), recipient (population characteristics), intensity (number of patient contacts), duration, and fidelity. Intervention content will be described using a

taxonomy of 93 discrete behaviour change techniques, a 19-item coding scheme to assess the extent to which theory has been used in the design of the intervention, and a set of nine items which specify the overarching function served by the intervention (e.g. to impart skills, to educate, to persuade, etc). Coding schemes for other dimensions will be developed inductively, iteratively and concurrently with the coding process, to ensure all possible elements contributing to effectiveness are extracted. This process will allow for the systematic identification of common and replicable elements of effective interventions; what works, for whom, and why? Insights from the coding process will be used as an evidence base to inform the content and theoretical basis of our intervention. If sufficient data are available, formal meta-analyses will be conducted of all interventions combined, with subgroup analyses to test whether effectiveness and betweenstudy heterogeneity vary according to the presence versus absence of discrete elements of each of the seven coded dimensions. Should meta-analysis be unfeasible due to lack of data, the relationship between intervention components and effectiveness will be explored by tabulating the presence of each coded component in effective versus ineffective interventions. Reporting will follow PRISMA guidelines for RCTs and meta-analysis. The review of the qualitative studies will consider first issues of validity and reliability and then use techniques of meta-ethnography to identify recurring explanatory concepts contributing to judgements of appropriateness, acceptability, efficiency and effectiveness of interventions from a variety of perspectives including the older people. The policy review will use documentary analysis methods successfully used in other NIHR funded studies, focusing on policy relevant to those with early or pre-frailty, and factors that might affect widespread implementation of a successful intervention. A narrative review will be presented of the qualitative evidence and the policy review.

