# 9. Health technologies being assessed

This study's aim is to develop, manualise and feasibility test a new health technology. The intervention development will follow MRC guidance for the development of complex interventions. Components of the intervention will be clearly specified following the development stage including the evidence review and empirical qualitative study of 'active ingredients' of effective interventions, and the intervention delivery defined by the co-design process. It will be based on a theoretical framework, including an assets-based approach and the Baltes' model of selective optimisation and compensation (see description below). The theoretical framework underpinning past effective interventions determined by our evidence review will also be considered. Components are likely to include initial assets/risk profile; the older person identifying and selecting life goals to optimise; behavioural techniques to optimise these goals, promoting coping and the maintenance of function; development of compensatory mechanisms to address deficits. The behavioural techniques used will be those demonstrating the best evidence of effectiveness with this population in the evidence review, or if a lack of evidence for those with early frailty, then effective techniques with other similar populations. The intervention could include an assets based approach identifying what older people are able to do and wish to continue, with the older person setting goals, problem-solving to support optimisation of these goals and behaviour change, and signposting/facilitation of use of services to aid compensatory mechanisms, such as mobility aids, technology, or low vision services. For example, an asset might be identified that the older person can still get a taxi to visit their daughter/grandchildren, although this is becoming increasingly difficult with tiredness/weakness (a feature of frailty) and concerns about occasional urinary incontinence. In order to preserve this asset, the intervention might include advice and goal setting on physical activity/resistance training and diet to increase strength, a problem solving approach to support change/coping and signposting on provision of incontinence pads as a compensatory mechanism.

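### The evidence review's fallback sorts trials into 'effective' and 'ineffective' and counts components, discarding effect size and precision when data are sparse, and its output is carried into the intervention

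*Protocol*

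**What the plan says.** All references are to the protocol.

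Section 15 (Data analysis, Systematic reviews) codes each trial's intervention on seven dimensions. Intervention content alone uses a "taxonomy of 93 discrete behaviour change techniques", "a 19-item coding scheme to assess the extent to which theory has been used in the design of the intervention", and "a set of nine items which specify the overarching function served by the intervention". For the rest, "Coding schemes for other dimensions will be developed inductively, iteratively and concurrently with the coding process".

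Two analysis routes follow. If data suffice, meta-analysis is done with "subgroup analyses to test whether effectiveness and betweenstudy heterogeneity vary according to the presence versus absence of discrete elements". If they do not, "the relationship between intervention components and effectiveness will be explored by tabulating the presence of each coded component in effective versus ineffective interventions". The section gives no definition of 'effective', no minimum number of trials per component, no significance level and no limit on the number of comparisons.

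The results are then used. Section 9: "The behavioural techniques used will be those demonstrating the best evidence of effectiveness with this population in the evidence review", with recourse to similar populations where evidence in early frailty is lacking. Section 14 (Intervention development) lets the co-design panels refine the intervention "while retaining the key intervention components (identified in the systematic reviews".

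**The concern.** A trial's result is an estimate with a standard error. The fallback replaces it with a label. If the label follows statistical significance, it depends heavily on trial size, so a component used mostly in large trials looks active and one used mostly in small trials looks inert, whatever their true effects. If the label follows the direction of the point estimate, about half of all trials with no true effect count as 'effective'. Either way, the fallback is used when data are too few to pool, which is when a binary label is least reliable.

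The number of comparisons adds to this. With well over a hundred codes and perhaps a few dozen trials, some components will be commoner in the 'effective' pile by chance. What is at stake is the component evidence behind the manual: a useful technique may be dropped, or one carried by chance or by trial size may be kept as a key component.

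**Working it through.** The protocol gives no error rate, alpha, trial count or trial size for the review, so there is no figure of its own to reproduce.

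**1. Number of coded elements (Section 15).** 93 + 19 + 9 = 121 content elements, plus an open number of inductive codes for the other dimensions.

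**2. How often significance mislabels a useful trial.** Assume a true effect d = 0.3 SD, n per arm and two-sided alpha 0.05. By the normal approximation, the miss rate is 1 − Φ(d√(n/2) − 1.96).
- n = 50: 0.3 × √25 = 1.50; Φ(1.50 − 1.96) = Φ(−0.46) ≈ 0.32; miss rate 68%.
- n = 100: 0.3 × √50 = 2.12; Φ(2.12 − 1.96) = Φ(0.16) ≈ 0.56; miss rate 44%.

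The t-test gives the same rounded figures. At d = 0.5 the t-test miss rate is 30% at 50 per arm and 66% at 20 per arm.

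A simulation makes the same point for a set of trials. Assumptions: 25–300 per arm, common mean effect 0.25 SD, between-trial SD 0.1. Only about 42% of trials were significant in the favourable direction, although the interventions worked on average.

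**3. Chance associations if components are tested.** For m independent tests at an assumed alpha of 0.05 with no component having an effect, P(at least one) = 1 − 0.95^m.

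| m | P(at least one) | Expected number |
|---|---|---|
| 10 | 0.40 | 0.5 |
| 20 | 0.64 | 1.0 |
| 40 | 0.87 | 2.0 |
| 121 | 0.998 | 6.05 |

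At alpha 0.01 and m = 121 the figure is 0.70. The table counts both directions. Counting only favourable associations at m = 121 gives 1 − 0.975^121 = 0.95, with 121 × 0.025 = 3.0 expected.

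Independence with every code testable is an upper-end case: many codes will be too rare to test, and all tests share the same trial results. Two null simulations relax it.
- 10–60 trials, 121 codes (rare or common, correlation 0 or 0.3), testable if present in and absent from at least 2 trials: at least one |z| > 1.96 in 52–98% of runs, and at least one Fisher exact p < 0.05 between the two piles in 19–99%.
- 10, 20 or 40 trials, code prevalence 10–50%, testable if present in and absent from at least 3 trials. With 20–40 codes: 27–43% at 10 trials, 49–62% at 20 and 59–76% at 40. With 121 codes: 58–94%.

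**4. Chance associations if components are only tabulated.** A table has no error rate until someone decides how to read it. If a component counts as favoured when it is at least 20 percentage points commoner in 'effective' trials, the first simulation gives at least one such component in 86–100% of null runs. That threshold is an assumption and drives the result. With 10 trials, 4 of them 'effective', a component present in 3 trials clears it when at least 2 of the 3 are 'effective' (2/4 = 50% against 1/6 = 17%). The chance of this with no true association is [C(4,2)·C(6,1) + C(4,3)] / C(10,3) = (36 + 4)/120 = 33% for that single component.

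**The case against.** The strongest reply is that nothing in the protocol makes a count or a p-value the rule for choosing components. The fallback is worded as exploration. Section 9 fixes an assets-based framework and a model of selective optimisation and compensation in advance. Section 14 combines the review with qualitative findings by thematic analysis and takes the result through several rounds with co-designers who interpret the evidence. Section 6 calls the review's output only probable active ingredients. Section 12 promises a separate published review protocol using Cochrane methods, and Section 24 promises PROSPERO registration. A definition of 'effective', a minimum trial count and multiplicity limits could sit there. Section 15 also does not say that all 121 codes will be tested.

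Much of this stands. A reader might infer that the review will nearly always name false active components, or that the table alone decides the manual's content. The documents support neither. The first depends on an assumed alpha, trial count and 20-point threshold, and for subgroup tests on 20–40 codes the figure falls to 27–43% at 10 trials. The second ignores the other sources that shape the intervention. Nor should silence here on multiplicity be read as a decision against control.

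The reply does not reach the tabulation itself, which Section 15 states as the method. Calling it exploratory helps little when Section 14 then says the review's components are retained through co-design. Nor does lack of data for pooling excuse it: trials that cannot be pooled often still report their own estimates.

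**Conclusion.** The point holds as a weakness of a stated method. Dividing trials into two undefined piles discards effect size and precision in the sparse setting where the fallback applies. Under a significance reading it misfiles a true 0.3 SD effect 68% of the time at 50 per arm and 44% at 100 per arm; effect, trial sizes and alpha are assumptions. Some chance associations among 121 or more codes are likely, but no single probability can be given, because the trial count, alpha and reading rule are not in the protocol.

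The consequence is limited to the component evidence that feeds intervention development. A reader might go further and infer that the feasibility trial is compromised. It is not: randomisation, outcomes, the descriptive analysis and the Section 16 success criteria do not depend on how components were chosen.

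**What to change.** In Section 15, replace the effective/ineffective tabulation. For each component, display every trial's effect estimate and confidence interval on one pre-named outcome, marked by whether the component was present or absent. Where no estimate can be extracted, show direction of effect with trial size. State that no trial is labelled ineffective because its result was non-significant. Report how many components were compared.

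In Section 14, describe the review's components as candidates, shown with their uncertainty for the co-design panel to weigh, and not as components that must be retained. The wording on best evidence in Section 9 should be read in the same way.

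A minimum number of trials per component and false discovery rate control would be sensible in the review protocol, but the latter is a preference and not needed to repair the stated method.

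The cost is wording changes, slightly more data extraction (an estimate and standard error per trial) and a more cautious claim about what works. No participants are needed and the trial design does not change.
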